Septic shock continues to exert a large economic burden around the world. In the United States, epidemiologic data indicate a clustering effect of sepsis, and in particular, a strong clustering in the Central Appalachia region, a region served by University of Kentucky HealthCare. Several developments have occurred that lead to the current study. First, angiotensin II is the newest FDA approved vasopressor agent indicated for use in vasodilatory shock. Several subgroups from the approval trial (ATHOS-3), have indicated that angiotensin II may confer a survival benefit in certain conditions, including those patients requiring continuous renal replacement therapy, those with altered angiotensin I: angiotensin II ratios, and most recently, those with elevated renin levels (which may serve as a surrogate for dysfunctional angiotensin I: angiotensin II ratios). Importantly, renin, angiotensin I, and angiotensin II levels are not readily available in-house.

Although angiotensin II is an FDA approved drug for vasodilatory shock, including septic shock, it was not added to the formulary at UK HealthCare and is thus not part of the current standard of care for a patient with septic shock requiring vasopressor therapy. During review at UK HealthCare ICU Committee meeting, the medication was not added to formulary due to concerns for cost, uncertainty regarding its place in therapy, and inability to restrict the drug only to sepsis patients within the healthcare enterprise.

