Community-Based Participatory Research: If you are conducting [community-based participatory research \(CBPR\)](#), describe strategies for involvement of community members in the design and implementation of the study, and dissemination of results from the study.

Research Repositories: If the purpose of this submission is to establish a Research Repository (bank, registry) indicate whether the material you plan to collect would or would not be available from a commercial supplier, clinical lab, or established IRB approved research repository. Provide scientific justification for establishment of an additional repository collecting duplicate material. Describe the repository design and operating procedures. For relevant information to include, see the UK Research Biospecimen Bank Guidance [\[PDF\]](#) or the UK Research Registry Guidance [\[PDF\]](#)

This will be a pre-post study built to replicate the introduction of angiotensin II into the clinical practice at UK HealthCare as outlined in the study protocol. 10 patients will be recruited, who receive normal standard of care, and consented to obtain plasma renin levels and biomarkers of renal function (three blood draws). After 10 patients, the next 20 patients meeting eligibility criteria will receive angiotensin II, they will also have blood drawn (four blood draws) to evaluate renin and renal biomarker response to angiotensin II.

Attachments

[Back to Top](#)

Study Population: Describe the characteristics of the subject population, such as anticipated number, age range, gender, ethnic background and health status. Identify the criteria for inclusion and exclusion. Explain the rationale for the use of special classes such as fetuses, pregnant women, children, institutionalized, adults with impaired consent capacity, prisoners, economically or educationally disadvantaged persons or others who are likely to be vulnerable.

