Once subjects are identified per the above process, an assessment will be made as described in form T by the study team member of whether the patient can provide informed consent. If ineligible, a legally authorized representative will be approached regarding the study. Informed consent will be sought once the patient meets the eligibility criteria as defined in the study protocol. If the legally authorized representative is not physically in the hospital due to visiting restrictions due to COVID-19, an electronic consent process will be sought as follows. The patient's LAR will be contacted via telephone and approached about the study in the same way that the LAR would be if they were physically present. If the LAR is interested in pursuing further, a member of the study team will send the LAR a RedCap link (<https://redcap.uky.edu/redcap/surveys/?s=7LWKY4JETE>) that has been designed for e-consent in this study. A member of the study team will walk the LAR through the e-consent document, which mirrors the written informed consent document exactly, and answer any questions along the way. If the LAR consents, they will sign the document using the e-sign feature in RedCap. A member of the study team will email the LAR back with a copy of the signed e-consent form.

[Back to Top](#)

Research Procedures: Describe the research procedures that will be followed. Identify all procedures that will be carried out with each group of subjects. Differentiate between procedures that involve standard/routine clinical care and those that will be performed specifically for this research project.

Control group (n=10): Standard of care will be followed for all aspects of care. The only procedure specifically involving research will be blood collection once the patient meets inclusion criteria (time T), 24 hours later (time T + 24 hours), and when the patient no longer requires vasopressor agents to support their blood pressure (defined as off of vasopressors for at least 4 hours). If the patient ceases vasopressor agents within 12 hours of the second blood draw, the third and final blood draw will not be collected.

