Intervention group (n=20): Standard of care will be followed for the management of septic shock. At which point the patient meets the inclusion criteria of the study, the patient's treating physician will be approached about the opportunity to offer angiotensin II to the patient. If the treatment team wishes to pursue, the patient or their LAR will be approached for written informed consent. Angiotensin II will be dosed per the protocol, and the patient will receive blood draw at the time they meet inclusion criteria (time T), 3 hours later (T+3), and 24 hours from angiotensin II initiation (T+24 hours), and when the patient no longer requires vasopressor agents to support their blood pressure (defined as off of vasopressors for at least 4 hours). If the patient ceases vasopressor agents within 12 hours of the third blood draw, the fourth and final blood draw will not be collected. All other aspects of the patient's care will be per the standard of care in the medical intensive care unit. Blood samples will be centrifuged, plasma extracted, and stored at -80 C. Commercial ELISAs will be used for analysis of renin and renal biomarkers (cystatin C, NGAL, renin, angiotensin II, angiotensin 1-7). COVID specification. Testing positive is a known exclusion criteria for the study. If a patient has results when evaluated for the study, this will be straightforward. However, if the test is pending while the patient is eligible for study entry, this will not make the patient ineligible for the study. If, in the opinion of the attending physician, COVID-19 is highly likely the patient will not be approached for informed consent. Otherwise, if COVID-19 test is pending, the patient or LAR will be approached for informed consent. If the test results as negative, study procedures will be performed as planned. If the test returns positive, the patient will be informed and dropped from the study. We will use their baseline information collected up to that point, but they will no longer receive blood draws or study medication (angiotensin II) once confirmed COVID positive. A case series of angiotensin II has been published in COVID 19

patients, and given the acuity of the disease state in question, it would not be appropriate to wait for a negative COVID test in our judgement.

Attachments

Data Collection: List the data or attach a list of the data to be collected about or from each subject (e.g. interview script, survey tool, data collection form for existing data).

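### The intervention arm's 3-hour sample is timed from meeting inclusion criteria rather than from the start of angiotensin II, so drug exposure at that draw is 3 h minus an unstated lag

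*Combined protocol and SAP*

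**What the plan says.** Research Procedures, intervention group, sets the sampling clock in one sentence: "the patient will receive blood draw at the time they meet inclusion criteria (time T), 3 hours later (T+3". T is therefore the moment of eligibility. The sentence then places the next sample at "24 hours from angiotensin II initiation (T+24 hours", which names drug start as the clock while keeping the label T.

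The same paragraph puts two steps between eligibility and treatment. First, "the patient's treating physician will be approached about the opportunity to offer angiotensin II to the patient". Then: "If the treatment team wishes to pursue, the patient or their LAR will be approached for written informed consent". The Informed Consent Process section agrees on the order: "Informed consent will be sought once the patient meets the eligibility criteria as defined in the study protocol". For a representative who is off site it describes a remote route ("The patient's LAR will be contacted via telephone and approached about the study in the same way"), followed by an electronic link, a guided reading and an e-signature. No maximum time from eligibility to infusion is given.

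The study design text states what the treated patients' samples are for: "they will also have blood drawn (four blood draws) to evaluate renin and renal biomarker response to angiotensin II". The control group is sampled at eligibility, 24 h after eligibility, and once off vasopressors, with no 3 h draw.

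**The concern.** A sample meant to show early response to a drug should sit at a known time after the drug starts. Here the written clock starts earlier, at eligibility, and the interval in between depends on how quickly the team decides and the patient or representative consents. Two treated patients sampled exactly on schedule could have quite different infusion times behind the same T+3 label.

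This is the only draw between baseline and 24 h in the treated arm. If exposure varies from patient to patient, the early change in renin and the renal biomarkers mixes different durations of treatment, and a small early change becomes harder to interpret. The early angiotensin II level, which is among the assays, also needs the infusion time to be read properly.

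**Working it through.** The plan states no figure for this point, so there is none to reproduce. The check compares the written rules and then does the timing arithmetic.

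**Inputs from the documents**
- Early draw: 3 h after T, with T defined as meeting inclusion criteria (Research Procedures, intervention group).
- 24 h draw: 24 h after angiotensin II initiation in the intervention arm (same sentence), and 24 h after eligibility in controls (Research Procedures, control group).
- Order of steps: eligibility, physician approach, consent, drug (Research Procedures; Informed Consent Process).

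**Assumed input**
- *d*, the hours from eligibility to infusion start. The documents do not give it. The range shown is 0 to 6 h.

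**Literal reading: T is eligibility**

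Exposure at the early draw = max(0, 3 − *d*). The treated arm's 24 h draw falls 24 + *d* hours after eligibility, against 24 h in controls.

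| Lag *d* (assumed) | Exposure at T+3 | Share of 3 h | Treated 24 h draw, hours from eligibility |
|---|---|---|---|
| 0 h | 3 h | 100% | 24 |
| 0.5 h | 2.5 h | 83% | 24.5 |
| 1 h | 2 h | 67% | 25 |
| 2 h | 1 h | 33% | 26 |
| 2.5 h | 0.5 h | 17% | 26.5 |
| 3 h | 0 h | 0% | 27 |
| 6 h | 0 h | 0% | 30 |

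The rows at 3 h or more need care. A research draw cannot precede consent. If consent itself takes longer than 3 h, a T+3 sample could not properly be taken on time at all; it would be missing or late. A zero-exposure sample taken on schedule requires consent within 3 h and an infusion that starts at 3 h or later.

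**Second reading: the 3 h run from a first draw taken after consent**

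Let *g* be the hours from that first draw to infusion start. Exposure = max(0, 3 − *g*). Because the first draw follows eligibility, *g* is no larger than *d*, and the physician approach and consent time drop out. With *g* = 0.5 h, exposure is 2.5 h. It equals 3 h only if the infusion starts at the moment of the first draw.

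**Third reading: T is initiation**

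This is what the label on the 24 h draw implies. Exposure is then 3 h for every patient still on the infusion, but the reading contradicts the definition of T earlier in the same sentence.

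**Result**

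The three readings give three different exposures for the same label, and the text does not choose between them. Only the third, which conflicts with the stated definition, gives a fixed 3 h.

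**The case against.** The strongest reply is that this is a loose label and not a faulty schedule. The sentence follows directly on the mention of dosing, and its 24 h label treats T as initiation, so the authors may have meant 3 h after drug start. Since the first research sample must follow consent, staff would naturally count 3 h from that sample, and most of the consent delay would not be lost. The plan also signals urgency: it declines to wait for a pending COVID-19 result. Finally, a detailed protocol is listed as an attachment but is not among the documents, and it may define the sampling windows.

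Much of this stands. The practical loss may be mainly the interval from first draw to infusion, and the documents do not show how long that is. The drug's absence from the formulary ("it was not added to the formulary at UK HealthCare") might suggest a dispensing delay, but dispensing is nowhere a sequenced or timed step, so the point rests only on physician approach and consent. What does not stand is that the ambiguity is harmless: the written definition of T is eligibility, and counting from the first draw still differs from counting from the infusion. An attachment that is not in hand cannot settle the text that is.

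A reader might go further and infer three stronger things. The documents do not support them.
- *That the sample will usually be taken with little or no drug on board.* The text permits this but gives no lag, so its frequency is unknown.
- *That the early effect is diluted by a definite percentage.* That needs a distribution of lags, which is absent, and a summary by means. The Statistical Analysis section uses medians, interquartile ranges and the Mann-Whitney test.
- *That a null early result could never be separated from late dosing.* Angiotensin II is assayed at the sampling times and vasopressor dosing is on the Data Collection list. Both give some evidence of exposure, although endogenous hormone contributes to the assay and clock times of the draws are not listed.

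**Conclusion.** The point holds as an inconsistency in the sampling clock, with a real but bounded consequence. By its own definition of T, the plan allows exposure at the early draw to be anything from 3 h down to none, according to an unstated and uncapped lag. If the 3 h run from a post-consent first draw, the shortfall is only the gap between that draw and the infusion. The lags in the table are assumptions; the order of steps and the two meanings of T are in the text.

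The damage is confined to the treated arm's within-arm early response, which is descriptive. Both stated objectives are comparisons with control, and the analysis section names no within-arm test at 3 h. Because controls have no 3 h draw, no planned between-group test uses this sample. The same double meaning of T does reach the 24 h comparison, where treated patients are sampled 24 + *d* hours after eligibility and controls at 24 h. The two timing questions share one cause and should be settled together. The correction is worth making because it determines what the early sample measures and costs very little.

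**What to change.** Revise the intervention-group sampling text as follows.
1. Define one clock start for the intervention arm's timed research samples: the recorded start of the angiotensin II infusion.
2. Take the baseline research sample after consent and immediately before the infusion.
3. Time the early sample at infusion start + 3 h and label it that way.
4. Correct the T labels so that T has a single meaning, and in the same edit reconcile the 24 h anchor with that of the control group.
5. Add the clock times of eligibility, infusion start and every draw to the data collection list, so that actual exposure can be reported.

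The cost is protocol wording and a few recorded times, with no added draw, patient or assay. The drawback is practical: bedside staff must schedule the early draw from the infusion record, so its hour after eligibility will vary between patients. The change concerns research sampling only and leaves dosing and clinical care untouched.

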If the research includes survey or interview procedures, the questionnaire, interview questions or assessment scales should be included in the application (use attachment button below).

The data collection instrument(s) can be submitted with your application in draft form with the understanding that the final copy will be submitted to the IRB for approval prior to use (submit final version to the IRB for review as a modification request if initial IRB approval was issued while the data collection instrument was in draft form).

Note: The IRB approval process does not include a statistical review. Investigators are strongly encouraged to develop data management and analysis plans in consult with a statistician.

Demographics (age, sex, race, past medical history), chief complaint, sequential organ failure assessment score, vasopressor dosing, lactate, requirement for mechanical ventilation, requirement for renal replacement therapy, serum creatinine values, blood pressure. Monitoring of side effects including: venous thromboembolism, arrhythmia, extremity hypoperfusion, delirium, new ischemic event, new infection), and any others deemed pertinent per the institution that may be related to angiotensin II. Patient outcomes including: in-hospital mortality, ICU and hospital length of stay, acute kidney injury and needed for renal replacement therapy. Lab values for renin and functional biomarkers of renal function at the time points described (cystatin C, NGAL, angiotensin II, angiotensin 1-7).

Attachments

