[To view what materials are currently attached to your application, go to "Application Links" in the menu bar on the left and click "All Attachments".]

Attachments

Attach Type	File Name
AddInfoConsiderations	57411 [name].pdf

Statistical Analysis

Continuous data will be described using medians and interquartile ranges. Discrete data will be described as counts and percentages. Changes in biomarker measurements will be calculated by subtracting the biomarker measurement at subsequent timepoint from the baseline biomarker measurement at enrollment. Assuming non-normal distributions of biomarker measurements with extreme elevations as well as skewness of the data for lengths of stay, continuous variables will be compared using the Mann-Whitney U test while discrete data will be compared between groups using chi-squared or Fisher's exact test as appropriate. A p-value <0.05 will be considered statistically significant.

Interim Analysis

Following enrollment of the 10 patients in the control arm and 10 patients in the angiotensin II arm (i.e. half of the 20 patients that will ultimately receive the drug), we will evaluate the risk of venous thromboembolism and any additional reported thrombotic reports from the 10 patients that have received angiotensin II. Groups will be compared using a Fisher's exact test given the small sample size. Given the concern for safety, if the p-value is 0.15 or less with increased thrombotic events in the angiotensin II group, the open-label study will be stopped. For example, assuming a baseline rate of thrombotic events of 1/10 (10%) in the control arm, if 5/10 patients in the angiotensin II group (50%) experienced a thrombotic event, a Fisher exact test yields $p=0.141$ and the open-label use of angiotensin II would be stopped due to concern for safety. If thrombotic event differences do not meet this threshold, we will continue with the enrollment of an additional 10 patients to meet the 20 patient enrollment set.

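### The 24-hour sample is timed from eligibility in controls but from drug initiation in the angiotensin II arm, under the same T+24 label

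*Combined protocol and SAP*

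**What the plan says.** The sampling schedule is in the combined protocol and SAP, under Research Procedures.

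- **Control group (n=10):** "blood collection once the patient meets inclusion criteria (time T), 24 hours later (time T + 24 hours", then a last draw once the patient has been off vasopressors for at least 4 hours.
- **Intervention group (n=20):** "the patient will receive blood draw at the time they meet inclusion criteria (time T", then "3 hours later (T+3), and 24 hours from angiotensin II initiation (T+24 hours", then the same off-vasopressor draw.

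In both arms the last draw is skipped if vasopressors stop within 12 hours of the preceding draw.

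The Informed Consent Process section places consent after eligibility: "Informed consent will be sought once the patient meets the eligibility criteria as defined in the study protocol". In the intervention group the treating physician is approached first, then the patient or representative, and the drug follows.

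Statistical Analysis computes change by "subtracting the biomarker measurement at subsequent timepoint from the baseline biomarker measurement at enrollment" and compares continuous variables between groups by the Mann-Whitney U test. It makes no allowance for elapsed time. Objective 1 asks whether renin declines faster with angiotensin II than in controls.

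**The concern.** T is the same event in both arms. In the intervention group, the description of the 24-hour draw (counted from drug start) and its label (T+24) agree only if the drug starts exactly at T. The plan's own sequence of physician approach, consent and drug start makes that unlikely. As written, the interval from first draw to 24-hour draw is longer in the treated arm by whatever that lag is.

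Objective 1 is about the speed of decline, and the 24-hour draw is the only fixed-time follow-up that both arms share. The 3-hour draw exists only in the treated arm, and the off-vasopressor draw is timed by an event and may be skipped. A difference in interval at 24 hours would therefore enter the between-arm comparison of raw change directly. Data Collection lists "Lab values for renin and functional biomarkers of renal function at the time points described" but does not name draw times or drug initiation time, although initiation may be captured with vasopressor dosing. If the times are not recorded, the mismatch could not be measured afterwards.

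**Working it through.** The plan gives no figure on this point, so there is none to reproduce. The check sets the sampling rules side by side and then sizes the effect under stated assumptions.

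**Intervals as written.** Let L be the time in hours from T to drug initiation. The documents do not give L.

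| Sample | Control | Angiotensin II |
|---|---|---|
| First draw | T | T |
| 3-hour draw | none | T + 3, which is 3 − L after drug start |
| 24-hour draw | T + 24 | T + L + 24 |
| First draw to 24-hour draw | 24 h | 24 + L h |

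For L = 1, 2 and 3 h, the treated interval is 25, 26 and 27 h against 24 h.

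**Size of the shift with no drug effect.** Assume that renin changes proportionally by a ratio r per 24 h in both arms. The apparent change in the treated arm is r^((24 + L)/24) − 1. Both r and L are assumptions.

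| Assumed control change per 24 h | L = 1 h | L = 2 h | L = 3 h |
|---|---|---|---|
| 50% fall (r = 0.5) | 51.4% fall | 52.8% fall | 54.1% fall |
| 30% fall (r = 0.7) | 31.0% fall | 32.0% fall | 33.1% fall |
| Flat (r = 1.0) | no change | no change | no change |
| 30% rise (r = 1.3) | 31.4% rise | 32.9% rise | 34.3% rise |

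Worked example for r = 0.5 and L = 2: 0.5^(26/24) = 0.472, a fall of 52.8%, which is 2.8 points more than in controls. Across L of 1 to 3 h at r = 0.5, the excess is 1.4 to 4.1 points. The shift favours the drug if renin is falling, vanishes if it is flat, and goes against the drug if it is rising.

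The delay that moves the apparent fall by 5 points is 24 × (ln 0.45/ln 0.50 − 1) = 3.6 h for a 50% fall, and 24 × (ln 0.65/ln 0.70 − 1) = 5.0 h for a 30% fall. Five points is only a yardstick.

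**Effect on the planned test.** A simulation used 10 against 20 patients, log-normal baseline (log SD 1.0 or 1.5), log-change SD 0.5 or 0.8, the same trend in both arms, and a two-sided exact Mann-Whitney test at 0.05 on raw change. Each setting had 10,000 runs (Monte Carlo standard error about 0.2 points). All SDs, trends and delays are assumed, and two-sidedness is also an assumption because the plan does not state it. With a 50% fall, the false-positive rate is 4.8–5.0% with no delay and 5.5–5.8% at 3 h. Across all four trends and delays of 0 to 3 h it is 4.4–5.8%. A repeat run agreed within Monte Carlo error.

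**The 3-hour sample.** Read literally it is counted from T, so it falls 3 − L hours after drug start: 2 h after at L = 1, 1 h after at L = 2, and before drug start if L exceeds 3 h.

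**The case against.** The strongest reply is that this is a slip of wording with no demonstrated consequence. Study Design says patients are "consented to obtain plasma renin levels and biomarkers of renal function (three blood draws", which suggests that the first research draw follows consent. If so, the physician approach and consent fall before that draw, and only the time from draw to infusion start separates the arms. Delay, trend and SDs above are all assumed, the test stays near its nominal level, and the application lists an attached proposal, not reproduced here, that may define the times. All of this stands as to size. It does not remove the conflict between the control and intervention paragraphs, or the one between the description and label of the treated 24-hour draw.

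Some stronger readings are tempting, and the documents do not support them.

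- **Two baselines.** A reader might infer that Statistical Analysis uses a second baseline because it says enrollment rather than T. Each arm has one first draw, and enrollment most naturally names that sample. The term is loose, but it does not define another sample.
- **No anchor for the 3-hour draw.** The intervention paragraph does give one. Both its words and its label count from T. The only open question is whether that was intended.
- **Prompt drug start.** The phrase "given the acuity of the disease state in question" might be read as evidence of a short lag. It explains not waiting for a negative COVID-19 test and says nothing about the time from draw to drug.
- **A need for a different analysis.** A log ratio per hour would remove the shift in the estimate under proportional change. In the same simulations its false-positive rate was 4.7–5.9%, so it gains nothing in error rate, and it would need a rule for values below the assay limit.

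**Conclusion.** The 24-hour rule is wrong as written, and the point is minor. Confidence is high that the text conflicts and low on the size and direction of any effect.

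It would go too far to conclude that the comparison is biased in favour of angiotensin II or that the test is invalid. The first needs a falling renin trend and an appreciable lag, neither of which the documents state. The second is not borne out at lags up to 3 h, where the simulated error rate is at most 5.8%. What remains is a possible small shift in the estimated change, which becomes material only if the lag is long and renin is moving. The plan also names no primary timepoint, so the importance of the 24-hour sample rests on its being the only fixed-time follow-up common to both arms.

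**What to change.** 1. Reconcile the control and intervention paragraphs of Research Procedures to one time zero for the baseline-to-24 h interval in both arms. The actual baseline research draw is one example. The choice of anchor is for the investigators, provided that it is the same in both arms and the label matches the description.
2. Use that same term for baseline in Statistical Analysis.
3. Confirm whether the 3-hour sample is meant to be counted from T, given that it then falls 3 − L hours after drug start.
4. Add the actual times of T, each draw and drug initiation to Data Collection, and report the actual elapsed interval by arm.
5. Keep the planned Mann-Whitney comparison. A sensitivity analysis using actual elapsed time is optional.
6. If the attached proposal already defines these times, carry its wording into these sections.

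The cost is protocol wording and timestamp recording, with no extra patients or blood draws. If the baseline draw becomes time zero, the treated baseline may fall later after eligibility than the control baseline. The recorded times would show this.
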